### 7.1.2 Dispensation Schedule

- At the end of Visit 1, qualified subjects will be randomized and the first dose of study drug will be administered in office. A supply of ADX-102 Ophthalmic Solution (0.5%), ADX-102 Ophthalmic Solution (0.1%), or ADX-102 Ophthalmic Lipid Solution (0.5%) will be dispensed for dosing QID.
- At the end of Visit 2, the unused vials from their Visit 1 kit will be re-dispensed to subjects, and a second kit for dosing through Visit 3 will also be dispensed.
- At Visits 2 and 3, remaining/used study drug will be collected from subjects for drug accountability.
- Subjects will be instructed to not use study drug on the day of visits (Visit 2 and 3) prior to the visit.

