### 8.6.2 Discontinued Subjects

Subjects may be discontinued at any time prior to their completion of the study due to:

- adverse events;
- unmasking when medically necessary;
- protocol violations;
- administrative reasons (e.g., inability to continue, lost to follow up);
- sponsor termination of study;
- subject choice (e.g., withdrawal of consent); and
- other.

Note: In addition, any subject may be discontinued for any sound medical reason at the discretion of the investigator.

Notification of a subject discontinuation and the reason for discontinuation will be made to Ora and/or study sponsor and will be clearly documented on the eCRF.

Discontinued subjects will not be replaced.

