3.1 General Study Design

This is a Phase 2a, single-center, randomized, double-masked study designed to evaluate the safety, tolerability and pharmacodynamic activity of ADX-102 Ophthalmic Solution (0.5%), ADX-102 Ophthalmic Solution (0.1%), and ADX-102 Ophthalmic Lipid Solution (0.5%) in subjects with dry eye syndrome. Approximately 45 male and female subjects at least 18 years of age with a subject-reported history of dry eye in both eyes and meeting all other study eligibility criteria will be randomized to receive treatment ADX-102 Ophthalmic Solution (0.5%), ADX-102 Ophthalmic Solution (0.1%), or ADX-102 Ophthalmic Lipid Solution (0.5%) in a 1:1:1 ratio (approximately 15 subjects in each treatment group).

Study visits will be referred to in all tables and listings as the expected study day corresponding to the visit to enable reviewers to understand the assessment timing without referring to the protocol visit schedule. The following table shows the scheduled study visits, their planned study day (note that there is no Day 0 and that Day 1 corresponds to the day of randomization), and the acceptable visit window for each study visit:

Scheduled Visit	Planned Study Day	Visit Window
Visit 1	Day 1	N/A
Visit 2	Day 8	± 1 Day
Visit 3	Day 29	± 2 Days

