7.3 Safety

The Safety population includes all randomized subjects who have received at least one dose of the investigational product. Subjects in the Safety population will be analyzed as treated.

8. General Statistical Considerations

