12.2 Treatment Exposure

Extent of treatment exposure for completed or discontinued subjects will be calculated in days using the following:

Extent of Exposure (days) = Date of completion/discontinuation – date of Visit 1 (Day 1)

Extent of treatment exposure for subjects who were lost to follow-up will be calculated in days using the following:

Extent of Exposure (days) = Date of last recorded visit – date of Visit 1 (Day 1) + 1

Extent of treatment exposure (days) for each subject exposed to study drug will be summarized with continuous descriptive statistics for each treatment group, using the Safety population. A subject listing of treatment exposure will also be produced.

13. Efficacy Analyses

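### SAP 12.2 sets no one-day minimum, so a subject dosed in office and discontinued on Day 1 is reported with 0 days of exposure

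*SAP*

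**What the plan says.** SAP 12.2 has two formulas. For completed or discontinued subjects it is "Extent of Exposure (days) = Date of completion/discontinuation – date of Visit 1 (Day 1)". For subjects lost to follow-up it is "Extent of Exposure (days) = Date of last recorded visit – date of Visit 1 (Day 1) + 1". Neither carries a minimum. Section 12.2 then states: "Extent of treatment exposure (days) for each subject exposed to study drug will be summarized with continuous descriptive statistics for each treatment group". This summary is based on the Safety population, and a subject listing accompanies it.

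Four other passages bear on the point:

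- SAP 7.3: "The Safety population includes all randomized subjects who have received at least one dose of the investigational product".
- SAP 3.1, on day numbering: "note that there is no Day 0 and that Day 1 corresponds to the day of randomization".
- Protocol 7.1.2, on the end of Visit 1: "the first dose of study drug will be administered in office".
- Protocol 8.6.2: "Subjects may be discontinued at any time prior to their completion of the study due to" a list of reasons that includes adverse events.

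**The concern.** Together these passages allow a subject to be randomized, dosed in office and discontinued on Day 1. The first formula returns 0 days for that subject, although SAP 7.3 counts the subject as dosed and 12.2 includes the subject in a summary of those exposed. A subject who attended the same single visit, received the same in-office dose and was then lost to follow-up is reported with 1 day. The reported value then depends only on the reason for leaving.

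Safety and tolerability are stated objectives, and there are about 15 subjects per arm. A subject who stops after the first dose is one whom a tolerability reader is likely to look up. A listing that shows 0 days, and an arm minimum of 0, would misdescribe that subject.

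**Working it through.** **Inputs.** Both formulas are from SAP 12.2. Day 1 is the day of randomization and there is no Day 0 (SAP 3.1). The first dose is in office at the end of Visit 1 (Protocol 7.1.2). Treatment is planned for 28 days, from Visit 1 to Visit 3 (Protocol Synopsis). Visit 3 is Day 29 ± 2 and arms have about 15 subjects (SAP 3.1).

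**Formulas in study days.** Let k be the study day of the end date.

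- Completed or discontinued: k - 1.
- Lost to follow-up: k - 1 + 1 = k.

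**Reproducing the plan's own figure.** A completer at the planned Day 29 gets 29 - 1 = 28 days, which matches the planned 28. This is coherent with dosing, because Protocol 7.1.2 says: "Subjects will be instructed to not use study drug on the day of visits (Visit 2 and 3) prior to the visit".

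**Applying the rule, with and without a one-day minimum or a blanket +1.**

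| Case | SAP 12.2 | max(1, SAP value) | Blanket +1 on the first formula |
|---|---|---|---|
| Discontinued Day 1 after the in-office dose | 0 | 1 | 1 |
| Discontinued Day 2 | 1 | 1 | 2 |
| Discontinued Day 8 | 7 | 7 | 8 |
| Completed Day 27 | 26 | 26 | 27 |
| Completed Day 29 | 28 | 28 | 29 |
| Completed Day 31 | 30 | 30 | 31 |
| Lost to follow-up, last visit Day 1 | 1 | 1 | not applicable |
| Lost to follow-up, last visit Day 8 | 8 | 8 | not applicable |

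The minimum changes the Day 1 row only. A blanket +1 also repairs that row, but it moves the Day 29 completer to 29 days, away from the planned 28.

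**Size in an arm summary (illustration).** Assume 15 subjects, 14 at 28 days and one discontinued on Day 1. With n - 1 equal values and one value at distance d from them, the sample SD is d/√n.

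- Subject at 0: mean = (14 × 28 + 0)/15 = 392/15 = 26.13; SD = 28/√15 = 7.23; minimum 0.
- Subject at 1: mean = (14 × 28 + 1)/15 = 393/15 = 26.20; SD = 27/√15 = 6.97; minimum 1.
- Difference in means: 1/15 = 0.07 day. The median is 28 either way.

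Mean, SD, median, minimum and maximum are all reported statistics under SAP 8.4.

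**The case against.** The best defence is that the rule measures elapsed days. It reproduces the planned duration, and on that convention a same-day stop is 0 elapsed days. The subject still counts in n, appears in the listing and stays in the Safety population. There are no primary or secondary endpoints and no formal hypotheses, and the documents do not say how often a Day 1 stop would occur. All of this stands, and it keeps the severity low. It does not rescue the value of 0, because 12.2 labels the quantity extent of treatment exposure and summarizes it for subjects who were exposed.

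Redaction is a weaker defence. SAP 12.1 and parts of SAP 8.4 are blacked out, and a general day-count convention there cannot be excluded. But 12.2 shows no redaction and refers to no other convention.

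A reader might infer more than the documents support, in three ways:

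- *The missing +1 is an error for everyone in the first formula.* It is not. Completers who follow the instruction not to dose before Visit 3 correctly get 28 days at Day 29. The +1 for lost subjects counts a visit day on which dosing is planned: in office at Visit 1, and self-instillation at Visit 2 in the SAP 3.2 schedule. The one-day difference between the formulas is therefore not in itself a mistake.
- *The formula should run to the last dose, not to the discontinuation date.* The visible text promises no last-dose definition. The early-termination text in Protocol 8.3.1 governs when evaluations are done, not how dates are recorded. Sections that could hold dosing-date or handling rules are wholly or partly redacted (Protocol 8.5; SAP 8.2 to 8.4 and 12.1). The lost-to-follow-up formula does not track take-home dosing either, so replacing only one formula would mix definitions.
- *A 0 removes the subject from the safety analysis.* It does not. Membership depends on having received a dose, not on calculated exposure.

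**Conclusion.** The point holds, and the rule is wrong as written, with low severity. SAP 12.2 gives 0 days to a subject who received the first dose and was discontinued on Day 1, while the same section treats that subject as exposed and gives 1 day to a subject lost after the same visit.

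The error is one day for each such subject. It would show in the listing, the arm minimum and the SD, with about 0.07 day on the mean in the illustrative arm of 15. No visible test or rate uses exposure, so no comparison between arms is affected.

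This rests on two assumptions: that no redacted section overrides 12.2, and that at least one subject is dosed and discontinued on Day 1. If no such subject occurs, nothing reported changes.

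**What to change.** Keep both formulas in SAP 12.2 and add one sentence: for every subject who received at least one dose of study drug, extent of exposure is max(1, calculated value). Do not add a blanket +1.

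The cost is one sentence in the SAP and one line of programming. No new data are needed, because whether a subject was dosed must already be known to define the Safety population. Completers and subjects lost to follow-up keep their present values.

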13.1 Primary Analysis

There are no primary endpoints in this Phase 2a study.

13.2 Secondary Analyses

There are no secondary endpoints in this Phase 2a study.

14. Exploratory Analyses

The following exploratory endpoints will be tested:

- Ora Calibra® Ocular Discomfort Scale;

A large block of black redacted text, consisting of approximately 25 lines of text, rendered as a solid black rectangle. The redaction is irregular, with varying line lengths and some white space at the top and bottom.

A large block of black redacted text, consisting of approximately 20 lines of text, rendered as a solid black rectangle. The redaction is irregular, with varying widths and heights for the black bars, suggesting a manual or hasty redaction process.

[REDACTED]

14.6 Ora Calibra® Ocular Discomfort Scale

Ocular discomfort scores will be subjectively graded by the subjects using the Ora Calibra® Ocular Discomfort Scale at all scheduled visits. The ocular discomfort scale ranges from 0 to 4 where [REDACTED]

[REDACTED]

[REDACTED]

Continuous descriptive statistics, including 80% and 95% CIs, as well as changes from baseline will be summarized by treatment group and visit. Pairwise two-sample t-tests will be employed to compare the observed treatment means as well as the changes from baseline at each visit. The mean treatment differences, two-sided 80% and 95% confidence intervals (CIs) for the mean differences and p-values will be reported. Wilcoxon rank sum tests will be conducted as sensitivity analyses to assess robustness of the results. Changes from baseline will also be compared between treatment groups using an ANCOVA model that includes the baseline score as a covariate as an additional sensitivity analysis. All analyses will be performed on the ITT population with LOCF.

Ocular discomfort changes from baseline in the study eye will be displayed graphically in a bar chart with standard error bars by visit and treatment group.

[REDACTED]

[REDACTED]

[REDACTED]

[REDACTED]

[REDACTED]

A large black rectangular redaction box covers the majority of the page content, from approximately y=113 to y=886. The redaction is irregular, with jagged edges and some internal white space, suggesting it was created by a digital tool rather than a physical redaction. The redacted area contains several lines of text that are completely illegible.

A document page featuring 24 horizontal black redaction bars of varying lengths. The bars are positioned at regular intervals, with some being significantly longer than others. The first bar is relatively short, followed by a longer one. The third bar is the longest, extending across most of the page width. Subsequent bars are of varying lengths, with some being very short and others being longer than the first. The bars are black and contrast sharply with the white background of the page.

15. Safety Analyses

All safety analyses will be conducted using the Safety population.

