## 5.3 Inclusion Criteria

### Subjects must:

1. Be at least 18 years of age of either gender and any race;
2. Provide written informed consent and sign the Health Information Portability and Accountability Act (HIPAA) form;
3. Have a reported history of dry eye for at least [REDACTED] prior to Visit 1;
4. Have a history of use or desire to use eye drops for dry eye symptoms within [REDACTED] of Visit 1;
5. Report a score of [REDACTED] on the Ora Calibra® Ocular Discomfort & 4-symptom questionnaire in at least one symptom at Visit 1;
6. Have a Schirmer's Test score of [REDACTED] at Visit 1;
7. Have a tear film break-up time (TFBUT©) [REDACTED] at Visit 1;
8. Have a corneal fluorescein staining score of [REDACTED] in at least one region (e.g. inferior, superior, or central) at Visit 1;
9. Have a sum corneal fluorescein staining score of [REDACTED] based on the sum of the inferior, superior, and central regions, at Visit 1;
10. Have a total lissamine green conjunctival score of [REDACTED] based on the sum of the temporal and nasal regions at Visit 1;
11. Have at least one eye satisfy all criteria for 6, 7, 8, 9, and 10 above.

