2.4 Statistical Hypotheses

This is a Phase 2a study to assess the safety, tolerability and pharmacodynamic activity of ADX-102 Ophthalmic Solution in subjects with dry eye syndrome. There are no primary endpoints and no formal statistical hypotheses.

3. Study Design and Procedures

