8.4 Data Analysis Conventions

[REDACTED]

[REDACTED]

Summaries for continuous and ordinal variables will include the number of observations (n), arithmetic mean, standard deviation (SD), median, minimum, and maximum. Minima and maxima will be reported with the same precision as the raw values; means and medians will be presented to one additional decimal place than reported in the raw values. Standard deviations will be presented to two additional decimal places than reported in the raw values. Summaries for discrete variables will include frequency counts and percentages. All percentages will be rounded to one decimal place (i.e., XX.X%).

All statistical tests will be two-sided with a significance level of 0.05 ($\alpha = 0.05$) unless otherwise specified. Confidence intervals (CI) for differences between treatment groups will be two-sided at 80% and 95% confidence levels where appropriate. All p-values will be rounded to four decimal places; p-values less than 0.0001 will be presented as “<0.0001”; p-values greater than 0.9999 will be presented as “>0.9999”.

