10.2 Pretreatment Variables

Baseline disease characteristics will be summarized by treatment group using continuous descriptive statistics for Ora Calibra® Ocular Discomfort Scale, corneal sum and total fluorescein staining, conjunctival sum and total lissamine green staining, TFBUT, SANDE questionnaire, VA, tear osmolarity, unanesthetized Schirmer's test, OSDI®, and IOP.

11. Medical History and Concomitant Medications

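### SAP 14.6 leads the Ocular Discomfort comparisons with two unranked, unadjusted t-tests; a baseline-adjusted ANCOVA fitted per pair of arms would be the better lead, for a modest gain

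*SAP*

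**What the plan says.** SAP 14.6 sets out three kinds of between-arm comparison for this scale, which runs from 0 to 4:

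- **t-tests, with no sensitivity label:** "Pairwise two-sample t-tests will be employed to compare the observed treatment means as well as the changes from baseline at each visit". Mean differences, two-sided 80% and 95% intervals and p-values follow from these.
- **Wilcoxon tests:** "Wilcoxon rank sum tests will be conducted as sensitivity analyses to assess robustness of the results".
- **ANCOVA on change from baseline:** "using an ANCOVA model that includes the baseline score as a covariate as an additional sensitivity analysis".

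The readable text does not say which of the two t-tests is the main result, or whether the ANCOVA is one three-arm model or a separate fit for each pair. All analyses use the ITT population with LOCF.

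SAP 8.4 sets the interval levels: "Confidence intervals (CI) for differences between treatment groups will be two-sided at 80% and 95% confidence levels where appropriate". The baseline score is collected at Visit 1 and is already tabulated under SAP 10.2: "Baseline disease characteristics will be summarized by treatment group using continuous descriptive statistics for Ora Calibra® Ocular Discomfort Scale". Allocation is "in a 1:1:1 ratio (approximately 15 subjects in each treatment group" (SAP 3.1). SAP 2.4 states: "There are no primary endpoints and no formal statistical hypotheses".

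**The concern.** A reader of the study report will take the comparisons that carry no sensitivity label as the result. Here there are two of them, neither uses the baseline score as a covariate, and nothing readable says which to prefer. Three things follow.

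- **Choice of estimate.** Two unranked estimates leave room to choose between them after the data are seen.
- **Precision.** The change score is more precise than the observed mean only when r > k/2. Without r and k, the plan cannot know which t-test is the weaker one, and the weaker one can be much worse.
- **Chance imbalance.** With about 15 subjects per arm, a sizeable baseline difference between arms is not rare. Given such a difference, both unadjusted estimates are generally shifted.

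**Working it through.** **Plan figure.** The documents state 15 per arm, but no SD, correlation or target interval width for this scale is readable. There is therefore no plan figure to reproduce.

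**Inputs.** From the documents: n = 15 per arm, two-sided 95% and 80% intervals. Assumed: complete data, approximate normality, a common linear slope, r = 0.3 / 0.5 / 0.7, k = 1 / 0.8 / 0.6. Low k is plausible because the entry criterion in Protocol 5.3 ("4-symptom questionnaire in at least one symptom at Visit 1") may narrow baseline scores. Follow-up SD is set to 1, so widths are in follow-up SD units.

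**Variance of a pairwise difference, in units of 2/15**

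- Observed means: 1
- Change: 1 + k² − 2rk
- Per-pair ANCOVA: (1 − r²)(1 + 1/26), where the last factor is the average cost of estimating the slope from 30 subjects

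Using change or follow-up as the ANCOVA outcome gives the same adjusted difference once baseline is the covariate. The t quantiles are 2.0484 (28 df, t-test) and 2.0518 (27 df, per-pair ANCOVA).

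**95% half-widths**

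- Observed means: 2.0484 × √(2/15) = 0.748
- ANCOVA: 2.0518 × √(2/15 × 27/26) × √(1 − r²) = 0.7635 × √(1 − r²)
- Change: 0.748 × √(1 + k² − 2rk)

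| | r = 0.3 | r = 0.5 | r = 0.7 |
|---|---|---|---|
| Observed means | 0.748 | 0.748 | 0.748 |
| Per-pair ANCOVA | 0.728 | 0.661 | 0.545 |
| Change, k = 1 | 0.885 | 0.748 | 0.579 |
| Change, k = 0.8 | 0.806 | 0.686 | 0.539 |
| Change, k = 0.6 | 0.748 | 0.652 | 0.539 |
| Gain over better t-test, k = 1 | 2.6% | 11.6% | 5.9% |
| Gain over better t-test, k = 0.8 | 2.6% | 3.5% | −1.1% |
| Gain over better t-test, k = 0.6 | 2.6% | −1.4% | −1.1% |

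Example (r = 0.5, k = 1): 1 − 0.661/0.748 = 11.6%. A simulation of 40,000 trials per cell agrees: at k = 1 the ratio of ANCOVA width to the better t-test is 0.973 / 0.883 / 0.941.

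**Worst case.** Since (1 + k² − 2rk) − (1 − r²) = (k − r)² ≥ 0, neither t-test can have a variance below 1 − r². The most ANCOVA can lose on this calculation is the slope cost, 0.7635/0.748 = 1.021, or about 2%. That happens when a t-test is already optimal: observed means at r = 0, change at r = k.

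**Against the weaker t-test.** At k = 1, ANCOVA is 17.7% narrower than change at r = 0.3 (0.728 against 0.885). It is 27.1% narrower than observed means at r = 0.7 (0.545 against 0.748).

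**Imbalance.** The baseline difference between two arms has SD √(2/15) = 0.365 baseline SDs. P(|difference| > 0.5) = P(|Z| > 0.5/0.365) = 17% for a given pair, and 36% for at least one of the three pairs (simulated). Given a 0.5 SD imbalance, the observed-mean difference is off by 0.5r = 0.15 / 0.25 / 0.35. The change difference is off by 0.5(r − k): −0.35 / −0.25 / −0.15 at k = 1, −0.25 / −0.15 / −0.05 at k = 0.8, and −0.15 / −0.05 / +0.05 at k = 0.6. ANCOVA removes this error under a common slope.

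**Three-arm model with unequal variances.** These simulations take the pair of arms with follow-up SD 1 and let the third arm's SD differ.

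- Third-arm SD 1.3: the three-arm interval is 6% wider than the better t-test at r = 0.3, k = 1; 5% wider at r = 0.5, k = 0.8; 11% wider at r = 0.7, k = 0.8. It is still 4% narrower at r = 0.5, k = 1.
- Third-arm SD 1.5: 4 to 20% wider over r = 0.3 to 0.7 and k = 0.6 to 1.
- Third-arm SD 0.6: nominal 95% coverage falls to about 92%.

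The per-pair ANCOVA kept about 95% coverage throughout.

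**The case against.** The strongest case against acting is that no readable decision depends on the order. There are no primary or secondary endpoints, all three methods are already planned, and moving a label adds no data. Parts of SAP 8.4 and 14.6, and Protocol 10.4.8, are redacted, so a ranking or its rationale may exist out of sight. The gain also rests on r and k, which have to be assumed; at low k it vanishes or turns slightly negative, and LOCF is ignored. All of this stands. It limits the importance of the point but does not remove the value of naming one adjusted estimate in advance.

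Three stronger readings are tempting and are not supported:

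- **That the t-tests are biased or invalid.** Over repeated randomisation both are unbiased. The error described above is conditional on the imbalance that happens to occur.
- **That the plan ignores baseline.** It analyses change scores and already includes the ANCOVA.
- **That leading with ANCOVA is free and always narrower.** One degree of freedom is spent, and some cells above are negative. A single three-arm model looks better on paper, at 4.8 / 13.6 / 8.0% narrower than the better t-test for k = 1. Part of that comes from pooling variance over all arms rather than from baseline adjustment, and it needs similar residual variances. The arms differ in strength and in formulation, so this cannot be presumed.

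**Conclusion.** The point holds as a low-severity improvement to consider. It is firm on what SAP 14.6 says: the comparisons without a sensitivity label are unadjusted and unranked, and the ANCOVA comes after them. The size of the gain is conditional. Over the assumed r of 0.3 to 0.7 and k of 0.6 to 1, the per-pair ANCOVA runs from 11.6% narrower to 1.4% wider than the better t-test, with a ceiling on the loss of about 2%. The steadier benefits are a single pre-named estimate, protection from chance baseline imbalance, and not leading with whichever t-test proves less precise. The finding covers this scale only, since the methods for the other endpoints are redacted.

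**What to change.** In SAP 14.6:

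1. Name ANCOVA with the baseline score as covariate as the lead comparison at Visits 2 and 3, fitted for each pair of arms on the same two arms that each t-test uses.
2. Report adjusted differences with 80% and 95% intervals and p-values.
3. Keep the t-tests on observed means and on changes, and the Wilcoxon tests, as sensitivity analyses.
4. If one three-arm model is preferred, say so, state that it assumes similar residual variance in all arms, and specify how this will be checked.

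The cost is SAP wording. No extra data, subjects or type of analysis is needed. The statistical price is one degree of freedom per comparison.

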### 4 DESIGN

This is a Phase 2a, single-center, randomized, double-masked study designed to evaluate the safety, tolerability and pharmacodynamic activity of ADX-102 Ophthalmic Solution (0.5%), ADX-102 Ophthalmic Solution (0.1%), and ADX-102 Ophthalmic Lipid Solution (0.5%) in subjects with dry eye. Approximately 45 male and female subjects at least 18 years of age with a subject-reported history of dry eye in both eyes and meeting all other study eligibility criteria will be randomized to receive treatment ADX-102 Ophthalmic Solution (0.5%), ADX-102 Ophthalmic Solution (0.1%), or ADX-102 Ophthalmic Lipid Solution (0.5%) in a 1:1:1 ratio (approximately 15 subjects in each treatment group).

Subjects who terminate early during the treatment period will be asked to complete safety assessments (as listed in [Appendix 1](#)) prior to commencement of any alternative dry eye therapy (if at all possible). Subjects who are terminated early from the study will not be replaced.

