### Early Termination/Discontinuation

If a subject is discontinued from the study prior to Visit 3 (Day 29 ± 2), then all safety evaluations that are to be performed at Visit 3 (Day 29 ± 2)

should be performed on the day of discontinuation (early termination) or at the discretion of the investigator.

Adverse Events (both elicited and observed) and serious adverse events (SAEs) will be monitored throughout the study. The investigator will promptly review all adverse events (both elicited and observed) for accuracy and completeness. All adverse events will be documented on the appropriate source document and case report form.

If a female reports a pregnancy or has a positive pregnancy test during the study the investigator will notify Ora immediately. The investigator shall request from the subject and/or the subject's physician copies of all related medical reports during the pregnancy and shall document the outcome of the pregnancy. The investigator will retain these reports together with the subject's source documents and will provide a copy of all documentation to Ora. The pregnant subjects will be discontinued from the study as per the exclusion criteria.

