### **8.4.2 Unscheduled Visits**

These visits may be performed in order to ensure subject safety. All procedures performed at an unscheduled visit will be recorded in the source documents and on the Unscheduled Visit eCRF pages. Any procedure indicated in the eCRF that is not performed should be indicated as "Not done."

Evaluations that may be conducted at an Unscheduled Visit include:

- Slit-lamp Biomicroscopy;
- Visual Acuity;
- Intraocular Pressure;
- Urine Pregnancy Test;
- Undilated Fundoscopy;
- Assessment of Adverse Events;
- Assessment of concurrent medications and/or treatments; and
- Any other assessments needed in the judgment of the investigator.

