Analysis populations include the intent-to-treat (ITT) population, the per-protocol (PP) population, and the Safety population. The statistical analysis of safety data will be performed on the Safety population. The analysis of baseline and exploratory efficacy data will be performed on the ITT population, and may be performed on the PP population as sensitivity analyses if it differs substantially from the ITT population.

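### In the visible text of SAP 14.6 every Ocular Discomfort Scale analysis uses LOCF, so the two named sensitivity analyses cannot show whether the arm comparison depends on it (minor; optional improvement)

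*SAP*

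**What the plan says.** SAP 14.6 compares the arms in pairs with two-sample t-tests, on the visit scores and on the changes from baseline. Two further methods are labelled as sensitivity analyses: "Wilcoxon rank sum tests will be conducted as sensitivity analyses to assess robustness of the results", and changes are also compared "using an ANCOVA model that includes the baseline score as a covariate as an additional sensitivity analysis". The paragraph closes with "All analyses will be performed on the ITT population with LOCF". Subjects grade themselves on the "Ocular Discomfort Scale at all scheduled visits", which SAP 3.2 places at Days 1, 8 and 29.

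SAP 7 adds that the exploratory efficacy analysis "may be performed on the PP population as sensitivity analyses if it differs substantially from the ITT population". SAP 7.2 limits that population to completers without significant deviations. SAP 9 tabulates discontinuations and their reasons by arm.

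On early exit, Protocol 4 says "Subjects who terminate early during the treatment period will be asked to complete safety assessments" and points to Appendix 1 for the list. Protocol 8.3.1 (Early Termination/Discontinuation) says that if a subject is discontinued before Visit 3, "then all safety evaluations that are to be performed at Visit 3" should be done on that day or at the investigator's discretion. Protocol 8.4.2 permits, at an unscheduled visit, "Any other assessments needed in the judgment of the investigator". The scale is listed with the exploratory variables (Protocol 6.1.1) and not with the safety measures (Protocol 6.2, SAP 2.3).

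Not visible: SAP 8.2 (missing data), Protocol 10.4.3, parts of SAP 14, and Protocol Appendix 1.

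**The concern.** A sensitivity analysis is informative about an assumption only if it changes that assumption. The Wilcoxon test changes the distributional assumption and ANCOVA changes the baseline adjustment. Neither changes how a missing Day 29 score is filled in. If all three analyses agree, a reader may take the result as robust to dropout when that was never examined.

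At stake is the Day 29 difference between formulations. If LOCF carries Day 8 forward for a subject who leaves after Visit 2, that subject's score at the four-week comparison is about three weeks old. If dropout, or change after Day 8, differs between arms, the difference is shifted. SAP 9 would reveal unequal dropout, but no committed analysis in the visible text shows what it does to the comparison. An analysis chosen after unmasking would be post hoc.

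**Working it through.** **The plan's own figure.** 3 arms x 15 = 45 subjects, as stated. No SD, effect size, power or dropout rate is visible, so everything below except the 15 per arm is assumed.

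**Assumed inputs.** SD 1 at each visit; correlation 0.5 between Day 8 and Day 29; both arms improve by 1 SD by Day 29, half of it by Day 8; all dropout falls after Visit 2; LOCF carries the Day 8 score. Arm A has at least as many dropouts as arm B. Higher scores are worse (SAP 8.1), so a positive bias makes A look worse than it is.

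**LOCF bias.** Bias = [sum over A's dropouts of (Day 8 minus Day 29) - the same sum for B] / 15. Subtracting baseline does not alter it.

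- Dropout unrelated to scores: each dropout contributes 0.5. For 2 v 0, 2 x 0.5/15 = 0.07. For 4 v 1, (4 - 1) x 0.5/15 = 0.10. For 2 v 2 with equal change, 0.
- Worst Day 8 scorers leave: a dropout with standardised Day 8 score z contributes 0.5 + (1 - 0.5)z on average. The four largest of 15 standard normal values have expectations 1.736, 1.248, 0.948 and 0.715 (sum 4.646). For 2 v 0, (1 + 0.5 x 2.984)/15 = 0.17. For 4 v 1, [(2 + 0.5 x 4.646) - (0.5 + 0.5 x 1.736)]/15 = 0.20.
- Worst Day 29 scorers leave (score unrecorded), 4 v 1: each contributes 0.5 - 0.5z, so [(2 - 2.323) - (0.5 - 0.868)]/15 = 0.003. Two errors happen to cancel.
- 2 v 2 unrelated, with change after Day 8 of 0.5 SD in one arm and none in the other: 2 x 0.5/15 = 0.07.
- With a total improvement of 0.5 SD instead of 1 SD, the unrelated-dropout figures halve to 0.03 (2 v 0) and 0.05 (4 v 1).

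**Completers only, 4 v 1.** Worst Day 8 scorers leave: -0.5 x 4.646/11 + 0.5 x 1.736/14 = -0.15. Worst Day 29 scorers leave: -4.646/11 + 1.736/14 = -0.30.

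**Comparison with a repeated-measures model.** The model column is simulated: 20,000 trials per scenario, maximum likelihood, no baseline term.

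| Dropout after Visit 2 | LOCF | Completers | Model |
|---|---|---|---|
| 2 v 0, unrelated | 0.07 | not shown | 0.00 |
| 4 v 1, unrelated | 0.10 | 0.00 | 0.00 |
| 2 v 0, worst Day 8 | 0.17 | not shown | 0.00 |
| 4 v 1, worst Day 8 | 0.20 | -0.15 | 0.00 |
| 4 v 1, worst Day 29 | 0.00 | -0.30 | -0.24 |

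With baseline added to the model (8,000 trials, correlation 0.5 between all visits), the three 4 v 1 rows give 0.00, 0.00 and -0.22.

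**Do the named sensitivity analyses detect it?** In that baseline run the LOCF t-test on change and LOCF ANCOVA gave 0.101 and 0.098 (unrelated), and 0.195 and 0.195 (worst Day 8). A separate run used integer scores on the 0 to 4 scale, with assumed means of 3.0, 2.6 and 2.0 in both arms and dropout in one arm only. The t-test and ANCOVA were both biased by 0.08, 0.12 and 0.16 points for 2, 3 and 4 dropouts. With 4 dropouts the false-positive rates were 7.3% (t-test), 7.3% (Wilcoxon) and 7.5% (ANCOVA). The three move together.

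**Precision for scale.** 95% half-width: 2.048 x sqrt(2/15) = 0.75 SD. 80% half-width: 1.313 x sqrt(2/15) = 0.48 SD.

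**The case against.** The strongest objection is that the check may already exist out of sight. SAP 8.2 is where a missing-data rule would sit, and it is redacted, as are Protocol 10.4.3 and text around the SAP 14.6 paragraph. What carries forward, including whether an unscheduled score counts, may be defined there. This stands: the point covers only the visible text, and the Day 8 carry-forward used above is an inference.

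Second, the per-protocol analysis is a partial check. Substantial dropout would help trigger it, and it largely removes Day 29 carry-forward. With unrelated dropout it is unbiased. When the worst Day 8 scorers leave (4 v 1), LOCF at +0.20 and completers at -0.15 bracket the truth. But it is optional, it also drops subjects with deviations, and it is itself biased in that case.

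Third, the harm is small. In 12 normal-score scenarios the LOCF 95% interval covered the truth 94.6% to 96.2% of the time; the 4 v 0 integer-score run above is harsher. A 4 v 1 split is 27% v 7% dropout in four weeks, for which the documents give no support. LOCF also has the smaller root-mean-square error in four of six comparisons with the model without baseline. For 4 v 1 these are: unrelated 0.380 v 0.397; worst Day 8 0.410 v 0.399; worst score at exit 0.379 v 0.412; worst Day 29 0.361 v 0.447. For 2 v 0 they are: unrelated 0.370 v 0.376; worst Day 8 0.396 v 0.375. This stands, and it is why the point is minor and LOCF stays.

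A reader might also infer that early terminators never give a discomfort score. The documents do not establish that. Protocol 4 defers to Appendix 1, which is not in the supplied text, and Protocol 8.4.2 leaves room for other assessments.

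**Conclusion.** The point holds in limited form. In the visible text, agreement among the t-test, Wilcoxon and ANCOVA results would say nothing about LOCF, because all three share it. Under the assumed inputs the effect is about 0.07 to 0.20 SD when dropout is unequal and either unrelated to scores or driven by Day 8 scores. It is zero when dropout and change are equal. The largest value is about 40% of the 80% half-width (0.20/0.48) and 27% of the 95% half-width (0.20/0.75).

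Two stronger conclusions are tempting and not supported. One is that the SAP has no check on missing data at all: the per-protocol option exists, and the sections most likely to hold such a check are redacted. The other is that LOCF should be replaced: each method fails under a different dropout mechanism, and LOCF often has the smaller total error.

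The endpoint is exploratory, and SAP 2.4 states that there are no primary endpoints and no formal hypotheses. This is an optional improvement. It is closed if a redacted section already commits to an observed-data analysis.

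**What to change.** **SAP 14.6.** Keep the LOCF analyses as written. Commit to one further sensitivity analysis on the observed scheduled-visit scores at Visits 2 and 3: a repeated-measures model with arm, visit, arm-by-visit and baseline, and small-sample degrees of freedom. Report it beside LOCF, with the number of carried-forward values by arm and visit. State that it accompanies LOCF, since it is biased by about -0.2 SD if unrecorded Day 29 scores drive dropout.

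**Cost.** SAP wording and a little more analysis work. The added estimate can be slightly less precise: the simulated SD of the difference, from the model without baseline, is 0.40 v 0.37 for LOCF with 4 v 1 unrelated dropout.

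**Secondary: a score at exit.** Check Appendix 1 first. If the scale is not already collected at early termination, consider adding it to Protocol 4 and 8.3.1, with study day and time since last dose recorded. Show it only as a flagged supplementary result. Protocol 7.1.2 and 8.3.1 have Visits 2 and 3 assessed without prior dosing that day, or after a wait of at least 4 hours, so an exit score may not be comparable. The gain depends on the mechanism. If an exit score midway between Day 8 and Day 29 is carried forward (4 v 1), LOCF bias falls from 0.10 to 0.05 SD (unrelated) and from 0.20 to 0.09 SD (worst Day 8). There is no gain if the score at exit or the Day 29 score drives dropout. The cost is one line in each of two protocol sections and a few minutes per early terminator.
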